#### **9.2.1.4. General Population Cohort**

- Randomly selected from general population and region-, age- and gender-matched to RA patient cohorts, up to 5 population controls per tofacitinib exposed patient.

#### **9.2.2. Exclusion Criteria**

Patients meeting any of the following criteria will not be included in the study:

1. Patients not meeting the inclusion criteria for the respective cohorts will be excluded.

### **9.3. Variables**

The study variables include baseline patient characteristics (ie, clinical and demographic characteristics, comorbidities and current and past therapies) and safety events of interest including, but are not restricted to, the following: serious infections, malignancies (including lymphoma subtypes and lung cancer), CV events (including MACE), and VTE (DVT and PE).

#### **9.3.1. Baseline Data**

Examples of baseline data captured in ARTIS can be found in [Appendices 1 and 2](#), respectively. The data captured include, but are not restricted to, the following: age, sex, years since diagnosis, disease severity, drug history, comorbidities (eg, history of malignancies), current concomitant medications, history of serious infection, history of opportunistic infection, history of herpes zoster, history of fractures, ever malignancy events (i.e. history of malignancy excluding NMSC, and specifically history of NMSC, history of lymphoma and history of lung cancer), and history of therapeutic procedures.

To facilitate the evaluation of the safety endpoints of MI and MACE, the following CV risk factors will also be evaluated at baseline: age (patients  $\geq 65$  years versus  $< 65$  years) and history of the following conditions: chronic kidney failure, diabetes, hypertension, statin use (as a proxy for history of hypercholesterolemia), previous MI, coronary heart disease, stable

angina pectoris, and history of therapeutic procedures to treat cardiovascular disease (e.g. coronary artery bypass graft (CABG) and percutaneous coronary intervention (PCI)).

To facilitate the evaluation of the primary endpoint of VTE, the following VTE risk factors will be evaluated at baseline and/or, for some risk factors, within specific time periods prior to index date as specified: age, previous VTE, undergoing major surgery from date of hospital admission to one month after date of discharge, MI within previous 3 months prior to index date, heart failure, use of combined hormonal contraceptives or hormone replacement therapy within 3 months of index date, malignancy, diabetes mellitus, hypertension, inpatient care because of RA (i.e., RA as main diagnostic listing; from date of admission to date after discharge).

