For lymphoma, incidence rates will be stratified by lymphoma subtypes; not limited but including non-Hodgkin lymphoma (NHL), Hodgkin lymphoma, chronic lymphatic leukemia. Similarly, CV event rates will be stratified by type of event (e.g. myocardial infarction (MI), MACE, serious congestive heart failure). Further, for the outcomes of MI and MACE, incidence rates of the safety events of interest will be stratified by patients with  $\geq 1$  CV risk factors versus no CV risk factors. The rates of safety events of interest, including infections, MACE, MI, and malignancies excluding NMSC, will also be evaluated within the elderly aged  $\geq 65$  years. Descriptive data will be presented in the interim reports. Likewise, VTE event rates will be stratified by type of event (DVT and PE). Further, for the outcomes of VTE, incidence rates of the safety events of interest will be stratified by patients with  $\geq 1$  VTE risk factors versus no VTE risk factors.

At study completion, all descriptive and comparative data analyses will be presented in the final report.

If feasible, stratified analyses to estimate the incidence rates for VTE stratified by time periods defined by the changes in the SmPC for tofacitinib use in patients with VTE risk factors will also be conducted (i.e., time period prior to 31 January 2020 vs. time period after 31 January 2020). Additionally, if feasible, stratification of the incidence rates for malignancy excluding NMSC, lung cancer, lymphoma, MACE and MI by time periods defined by changes in the SmPC for use in patients with malignancy and CV risk factors will be conducted (i.e. time period after June 2021).

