
Notes: Analysis was only made for comparisons where both cohort had at least 5 observed events. HR: Hazard Ratio. CI: Confidence Interval.  HRa: stratified for year at start, adjusted for age and sex.  HRb: stratified for year at start, adjusted for age, sex, prior number of days in inpatient care, history of infection, cancer, MI, diabetes, COPD, and joint replacement surgery.  HRc: stratified for year at start, adjusted for age, sex, prior number of days in inpatient care, history of infection, cancer, MI, diabetes, COPD, and joint replacement surgery, Rheumatoid factor, HAQ(linear), RA disease duration, DAS28(linear), DMARDs, steroids. Complete case analysis.  HRd: as HRc but using a missing indicator, and quartiles, for HAQ and DAS28.
									

Table IV. Results from crude and adjusted Cox regressions comparing tofacitinib to biologic DMARDs (bDMARDs), stratified by the number of bDMARDs									
Outcome	Number of previous biologics	HRa	95% CI	HRb	95% CI	HRc	95% CI	HRd	95% CI
Each event	0								
	1								
	2								
	Aggregate estimate								

Notes: Analysis was only made for comparisons where both cohorts had at least 5 observed events. HR: Hazard Ratio. CI: Confidence Interval.  HRa: stratified for year at start, adjusted for age and sex.  HRb: stratified for year at start, adjusted for age, sex, prior number of days in inpatient care, history of infection, cancer, MI, diabetes, COPD, and joint replacement surgery.  HRc: stratified for year at start, adjusted for age, sex, prior number of days in inpatient care, history of infection, cancer, MI, diabetes, COPD, and joint replacement surgery, Rheumatoid factor, HAQ(linear), RA disease duration, DAS28(linear), DMARDs, steroids. Complete case analysis.
									

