	ARTIS		BIOBADASER, BSRBR, RABBIT
Event	Operationalization	Validation ICD	Operationalization (Final list TBD based on reported endpoints).
CV risk	Major Acute Cardiovascular Events (MACE), combines MI, stroke, and fatal cardiovascular events: I00-I99 as main cause of death, or I20.0, I21, I60-I64 as diagnosis in in- or outpatient care.	
See Serious Infections
 
‘Outcome’ was defined as any first-ever ACS event, which in turn was defined as a primary discharge diagnosis of acute myocardial infarction or unstable angina pectoris, or as acute myocardial infarction being the underlying cause of death. For discharge diagnoses, the date of admission to hospital was considered the event date. This outcome definition has previously been validated in a Swedish early RA cohort, with a positive predictive value of 95%. In addition, a regional validation study of hospitalized acute MI and stroke found positive predictive values of 96% and 94% respectively, in the period 1977 to 1987.
 
Lindblad et al. Validity of register data on acute myocardial infarction and acute stroke. Scandinavian Journal of Public health 1993; 21 (1):3-9.
	
Fatal and non-fatal
 
10000891 Acute myocardial infarction; 10006147 Brain stem infarction; 10006148 Brain stem ischaemia; 10008034 Cerebellar infarction; 10008088 Cerebral artery embolism; 10008120 Cerebral ischaemia; 10008190 Cerebrovascular accident; 10014498 Embolic stroke; 10019005 Haemorrhagic cerebral infarction; 10019016 Haemorrhagic stroke; 10024033 Lateral medullary syndrome; 10028596 Myocardial infarction; 10028602 Myocardial necrosis; 10033697 Papillary muscle infarction; 10043647 Thrombotic stroke; 10049768 Silent myocardial infarction; 10051078 Lacunar infarction; 10055677 Haemorrhagic transformation stroke; 10056237 Migrainous infarction; 10059613 Stroke in evolution; 10060839 Embolic cerebral infarction; 10060840 Ischaemic cerebral infarction; 10061256 Ischaemic stroke; 10062573 Brain stem thrombosis; 10064961 Thalamic infarction; 10066591 Post procedural stroke; 10066592 Post procedural myocardial infarction; 10067167 Cerebellar embolism; 10067347 Thrombotic cerebral infarction; 10067462 Millard-Gubler syndrome; 10068621 Cerebellar ischaemia; 10068644 Brain stem stroke; 10069020 Basal ganglia infarction; 10070671 Cerebral septic infarct; 10070754 Inner ear infarction; 10071043 Basal ganglia stroke; 10071260 Carotid angioplasty; 10073945 Perinatal stroke; 10074422 Brain stem embolism;
 
Fatal only
 
10002886 Aortic aneurysm rupture; 10003173 Arterial rupture; 10003210 Arteriosclerosis; 10003212 Arteriosclerosis moenckeberg-type; 10006145 Brain stem haemorrhage; 10007522 Cardiac asthma; 10007554 Cardiac failure; 10007556 Cardiac failure acute; 10007558 Cardiac failure chronic; 10007559 Cardiac failure congestive; 10007559 Cardiac failure congestive; 10007560 Cardiac failure high output; 10007625 Cardiogenic shock; 10007684 Carotid arterial embolus; 10007686 Carotid artery aneurysm; 10007688 Carotid

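### The closed list of CV risk factors used to split MACE rates omits previous stroke and heart failure, although MACE counts stroke and any cardiovascular death

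*Protocol*

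**What the plan says.** Protocol section 9.3.1 introduces the list with "To facilitate the evaluation of the safety endpoints of MI and MACE, the following CV risk factors will also be evaluated at baseline". It then gives age (65 and over versus under 65) and a history of "chronic kidney failure, diabetes, hypertension, statin use (as a proxy for history of hypercholesterolemia), previous MI, coronary heart disease", followed by stable "angina pectoris, and history of therapeutic procedures to treat cardiovascular disease (e.g. coronary artery bypass graft (CABG) and percutaneous coronary intervention (PCI". The list ends there. The general baseline list at the start of the same section is expressly open-ended; this one is not.

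The next paragraph of 9.3.1 gives a separate list for VTE, which contains heart failure: "MI within previous 3 months prior to index date, heart failure, use of combined hormonal contraceptives".

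Appendix 4 defines MACE as an endpoint that "combines MI, stroke, and fatal cardiovascular events: I00-I99 as main cause of death, or I20.0, I21, I60-I64" as a diagnosis in in- or outpatient care.

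Section 9.7.2 states that "for the outcomes of MI and MACE, incidence rates of the safety events of interest will be stratified by patients with" at least one CV risk factor against those with none ("CV risk factors versus no CV risk factors"). The abstract repeats this split.

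**The concern.** A stratum labelled as having no CV risk factors should not contain patients who have already had one of the events that the endpoint counts. The list respects this on the coronary side, with previous MI, coronary heart disease and stable angina. It does not do so for stroke, which is the other non-fatal component of MACE. Heart failure is also absent, although a death with heart failure as main cause falls within I00-I99 and is a MACE event, and although 9.3.1 already requires heart failure at baseline for VTE.

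At stake is the reading of the stratified MACE rates. If patients with a prior stroke or heart failure sit in the lower-risk stratum and have a higher MACE rate than the rest of it, the rate shown there is too high and the two strata look more alike than they are.

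**Working it through.** The plan states no figure for this point, so there is none to reproduce. The check compares the text and then illustrates the size.

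**Step 1: endpoint against list.**

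| MACE component (Appendix 4) | Prior form on the 9.3.1 CV list? |
|---|---|
| I20.0, I21 (unstable angina, MI) | Yes: previous MI, coronary heart disease, stable angina, procedures |
| I60-I64 (stroke) | No |
| I00-I99 as main cause of death | Partly: coronary disease and hypertension yes, heart failure no |

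**Step 2: does anything else in the protocol remove these patients?** Section 9.2.2 excludes only those who fail the cohort inclusion criteria, so prior stroke or heart failure does not exclude anyone. Section 9.4.3 names the Patient Register as a source of baseline comorbidities, covering inpatient and non-primary outpatient care. Section 9.9 gives smoking and the cholesterol/HDL ratio as examples of CV risk factors that cannot be adequately captured; it names neither stroke nor heart failure.

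**Step 3: apply the rule.** Take a 60-year-old with a previous stroke, no hypertension, diabetes or kidney failure, no statin, no coronary disease and no procedure. The count of listed factors is zero, so the patient is placed in the no-risk-factor stratum.

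**Step 4: size.** Let q be the share of that stratum's person-time from patients whose only risk factor is prior stroke or heart failure, and RR their MACE rate ratio against the rest of the stratum. If the rest have rate λ, the stratum rate is (1 − q)λ + q·RR·λ = λ[1 + q(RR − 1)].

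- Inflation of the stratum rate: q(RR − 1).
- Share of the stratum's events from misplaced patients: q·RR / (1 − q + q·RR).
- Observed contrast if the true ratio between strata were 3 (assumed), holding the other stratum's rate fixed: 3 / [1 + q(RR − 1)].

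The protocol gives neither q nor RR. Over an assumed q of 1% to 5% and RR of 2 to 5:

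| q | RR | Inflation | Share of events | Contrast of 3 becomes |
|---|---|---|---|---|
| 1% | 2 | 1% | 2.0% | 2.97 |
| 1% | 5 | 4% | 4.8% | 2.88 |
| 2% | 3 | 4% | 5.8% | 2.88 |
| 2% | 5 | 8% | 9.3% | 2.78 |
| 5% | 2 | 5% | 9.5% | 2.86 |
| 5% | 5 | 20% | 20.8% | 2.50 |

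With both conditions on the list, q is zero by definition.

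**The case against.** The strongest reply is that this is a descriptive split in a study without prior hypotheses, that overall MACE rates do not change, and that few patients are affected. To be misplaced, a patient must be under 65 and have none of the other listed factors. The procedures item is worded for cardiovascular disease in general and may catch a few more. All of this stands, and it is why the effect is probably modest.

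Heart failure is also the weaker half. If any I00-I99 death justifies a listing, other circulatory diagnoses could be argued for too. That is fair: stroke follows directly from the endpoint definition, whereas heart failure is a judgement, supported by its being collected already and by section 9.7.2 naming serious congestive heart failure as a CV event type.

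The amendment log attributes the February 2022 revision of the list to a PRAC request and clarification. The documents do not show what was asked for, so this neither defends nor condemns the omission.

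A reader might infer more than the text supports:

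- *That the two conditions are left out of all adjusted analyses.* The Appendix 2 Cox notes list "history of infection, cancer, MI, diabetes, COPD, and joint replacement surgery", but they belong to table shells described as a general outline. Section 9.7.2 leaves the final confounders to the SAP, which is not at hand.
- *That their absence from Appendix 2 Table I proves the point.* Table I also lacks chronic kidney failure and statin use, which 9.3.1 does list.
- *That the inflation is large.* A q of 2% with RR of 20 would give 38%, but nothing in the protocol supports such a ratio.
- *That one recurrent stroke would swing the tofacitinib rate.* With few expected events any single event does so; that reflects sparse data, not this omission.
- *That the strata were added to show whether excess risk is confined to patients with risk factors, or that label changes make the misplacement unequal across cohorts.* The protocol states neither.
- *That the MI strata are equally affected.* The mismatch is clear for MACE and weak for MI.

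**Conclusion.** The point holds for the MACE strata. The protocol fixes both the list and the split, and together they place a patient under 65 with prior stroke or heart failure and no other listed factor among those without CV risk factors. Provided such patients have a higher MACE rate than the rest of the stratum, the bias raises the no-risk-factor rate and pulls the contrast towards 1. Its size is not derivable from the protocol; the 1% to 20% range rests wholly on the assumed q and RR, and a modest effect is the more likely. This is a cheap correction worth making, not a threat to the study's main rates.

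**What to change.** In section 9.3.1, add previous stroke (the endpoint's own codes I60-I64, dated before index) and heart failure (using the variable already required for the VTE list) to the CV risk factors. Use the extended list for the MACE strata in all four cohorts and show both items in Appendix 2 Table I. Applying them to the MI strata as well is optional.

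The cost is two look-back variables for the CV list, one of them already planned for VTE, from a register that is already linked, and a short edit to 9.3.1 and Table I. The downside is a slightly smaller no-risk-factor stratum, and hence slightly less precise rates there.

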### 9.3.2. Follow-Up

Subjects will be followed from treatment start (or for comparator cohorts not defined by therapy: from an index date) until each outcome of interest, with death and emigration from Sweden treated as censoring events.

Some outcomes of interest in this study are thought to potentially occur at a higher rate while on drug, but that increased risk subsides after the drug is discontinued (ie, serious infections, herpes zoster, CV events, gastrointestinal (GI) perforation, progressive multifocal leukoencephalopathy (PML)). Those events will be evaluated over a risk window that includes time from drug initiation until 90 days after end of treatment. When a patient initiates a new therapy within the 90-day extension, the time and events during the overlapping period will be assigned to both treatments. The 90-day extension period is implemented in part to accommodate ongoing exposure to treatments with longer half-lives, and in part to ensure that any subclinical or undiagnosed illness at time of end of treatment is captured. As an additional sensitivity analysis for MACE, MI, serious infection, VTE, herpes zoster, PML, and gastrointestinal perforation events with a 90-day extension period applied after treatment discontinuation, if a new medication is started during the 90-day window after discontinuation of a previous medication, initiation of the new medication will stop the 90-day risk window, and any event prior to the new medication start will be assigned to the discontinued medication. Similarly, as part of the primary analysis, for malignancy and all-cause mortality events, a 90-day risk window will be applied to the censoring at switch approach (i.e., if a malignancy or death occurs in first 90 days after a patient has switched to a different therapy, follow-up time and the event will be attributed to prior therapy and not current therapy).

For non-melanoma skin cancer (NMSC), lung cancer, lymphoma and malignancies excluding NMSC, and all-cause mortality, the manifestation of which is expected to be delayed relative to the time of exposure, the outcomes will be evaluated using two different approaches, a once exposed always at risk approach as the primary analysis and a censor at switch approach as a secondary analysis. PML rates will also be described using this approach.

---

 The potential mechanism for increased PML risk is poorly understood. PML will be evaluated using both on drug and once-exposed always at risk approaches.

The primary analysis will assume a once exposed always at risk paradigm, as is frequently used in study of malignancy risk due to bDMARDs. Under this approach, follow up for each cohort continues from the cohort index date until the first of a malignancy event, loss to follow up, death or end of study. Follow up for each exposure cohort continues after switching to a new drug or discontinuation of treatment. This approach maximizes follow up time and the ability to capture long latency events, ie, events that occur or are detected years after exposure. Under this approach, events will be double-counted if a patient indexed to bDMARD switches to tofacitinib and a malignancy occurs subsequent to tofacitinib exposure. That is, the event will be assigned to both the bDMARD and the tofacitinib exposure cohorts as will the corresponding person years since index to the respective cohorts. Because tofacitinib is expected to be used as a later line therapy, switching is expected to be non-random with most tofacitinib patients having been included in the bDMARD cohort prior to initiation of tofacitinib. In such cases, the bDMARD rate will have more associated person-years and thus a relatively lower rate than the corresponding rate in the tofacitinib cohort.

Using this primary analytic approach, if neither tofacitinib nor bDMARDs cause an increased risk of malignancy both exposure cohort rates will reflect the background rates of malignancy from the time of index to the end of the study period and the comparative effect measure will indicate no difference in rates. If tofacitinib does cause an increased rate of malignancy, which is the effect we are most interested in detecting, a relatively higher rate will be observed in the tofacitinib exposed cohort. The once exposed always at risk approach is therefore able to detect an increased rate given the non-random switching expected to occur given use of bDMARDs prior to tofacitinib and is consistent with previous studies evaluating the risk of individual biologics. Additional analyses will be conducted to evaluate potential confounders and the impact of different latency assumptions as will be described in the statistical analysis plan (SAP). Sensitivity analyses will be conducted that restrict the bDMARD comparator cohort to patients who were never exposed to tofacitinib or other non-biologic advanced therapies and compare the characteristics of those bDMARD patients ever and never exposed to tofacitinib.

Secondary analyses that censor follow up time after a switch to a different treatment class will also be performed. Among patients indexed to a bDMARD cohort, follow up will begin at index and continue until the first of an event, switch to tofacitinib or other non-biologic advanced systemic therapy, loss to follow up, death, or study end date. Similarly, for tofacitinib, follow up will begin at index and continue until the first of an event, switch to a non-JAK inhibitor-based advanced systemic therapy, loss to follow up, death or study end date. While this approach eliminates the problem of double counting, it may not allow sufficient follow up time to allow for latent effects or detection and decreases the number of events included reducing the statistical power to detect a higher risk of malignancy in tofacitinib treated patients. However, under an assumption of no latency or a very short latent period as in an aggressive tumor promoter, this approach would detect an increased risk of disease on tofacitinib relative to the risk due to bDMARDs.

Of note, several studies compared a once-exposed approach to a time on drug and other approaches and found similar rates of malignancy using an on-drug and ever-exposed approach.

The schematic below provides examples of patterns of event and treatment patterns to illustrate resulting contribution to rate calculation in the once exposed always at risk and censoring at switch analytic models:

- \*: bDMARD index date;
- ~: year on bDMARD;
- ^: tofacitinib index date;
- : year on tofacitinib;
- O: discontinuation of advanced systemic therapies;
- =: year not on systemic therapy;
- X: event.

Treatment/Event pattern	Once-exposed always at risk		Censoring at Switch	
	bDMARD rate contribution (events/person years)	Tofacitinib rate contribution (events/person years)	bDMARD rate contribution (events/person years)	Tofacitinib rate contribution (events/person years)
* ~ ~ ~ ^ - - X	1/5	1/2	0/3	1/2
* ~ ~ ~ X	1/3	0/0	1/3	0/0
^ - - - O = = = X	0/0	1/6	0/0	1/6 a
* ~ ~ ~ ^ - - - ~ ~ ~ X	1/9	1/6	0/3	0/3
^ - - - - ~ ~ ~ X	0/0 b	1/7	0/0 b	0/4

- a. Patients continue to be followed after index exposure discontinuation if they do not initiate another systemic therapy in a different class.
  - b. Patients are ineligible for bDMARD cohort index after tofacitinib index.
- Note: if an event does not occur, person time will be allocated to rate denominator as described in table without corresponding event.

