#### 9.5. Study Size

All eligible patients in the Swedish registers will be included, with no upper limit on the sample size. The feasibility of more refined comparative analyses to evaluate safety concerns that adequately adjust for patient channeling and confounders will be assessed at an interim time point and after 7 years will be based on statistical power. Since the comparator groups will be a magnitude larger than the tofacitinib treated group, statistical power will be limited by the uptake of tofacitinib, which is difficult to estimate a priori. While the primary objective of the protocols is active surveillance, conducting quantitative, confounding controlled comparisons will depend on having a sufficient sample.

Table 2 and Table 3 below describe the power to detect a 2-fold difference in event rates between tofacitinib-initiators and bDMARD-initiators assuming the following:

- $\alpha=0.05$ ;
- 3 different bDMARD-treated patient population sizes (reflecting roughly range of EU registers):  $n=11100$ ,  $n=5050$ ,  $n=1650$ ;
- 4 different tofacitinib-treated patient population sizes:  $n=100$ ,  $n=250$ ,  $n=500$ ,  $n=1000$ ;
- Estimated rates on bDMARD of 30/1000 person years (PY) (eg, serious infection), 10/1000 PY (eg, malignancy excluding NMSC), and 6/1000 PY (eg, major adverse cardiovascular event (MACE)) based on previous analysis with registers (Pfizer, internal data);
- 7-year study period;
- Constant rate of accrual;
- 5% annual loss to follow up among tofacitinib-treated patients.

Additionally, Table 2 assumes a 0% annual rate of switching off tofacitinib, as would be true for a drug with very high persistence or for an analysis following the once exposed always at risk paradigm. Table 3 assumes a 30% annual rate of switching from tofacitinib to a bDMARD over the study period, as previously demonstrated in the EU for bDMARDs in Italy.

For an event with a rate of 30/1000 PY, such as serious infections, 250 patients would allow sufficient power to detect a 2-fold difference in rates between tofacitinib and bDMARD-exposed patients assuming very high persistence (Table 2), while 500 tofacitinib exposed patients would be nearly sufficient if 30% of tofacitinib treated patients switched off of tofacitinib annually.

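### In the censor-at-switch analysis of malignancy and mortality, the 90-day rule moves person-time only for patients who have an event, so numerators and denominators do not match at entry to or exit from tofacitinib

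*Protocol*

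**What the plan says.** All the relevant text is in Protocol section 9.3.2 (Follow-Up).

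- **90-day rule for malignancy and death under censoring at switch:** the trigger, and what is moved, read "if a malignancy or death occurs in first 90 days after a patient has switched to a different therapy, follow-up time and the event". As for where these go, the rule says that they "will be attributed to prior therapy and not current therapy". The sentence introduces this as part of the primary analysis, although the next paragraph names censoring at switch as the secondary approach.
- **bDMARD person-time:** "follow up will begin at index and continue until the first of an event, switch to tofacitinib or other non-biologic advanced systemic therapy". The other stopping points are loss, death and study end. No 90-day extension is given.
- **Tofacitinib person-time:** "for tofacitinib, follow up will begin at index and continue until the first of an event, switch to a non-JAK inhibitor-based advanced systemic therapy". The other stopping points are the same. No 90-day lag is given.
- **Event-free patients (note under the schematic):** "if an event does not occur, person time will be allocated to rate denominator as described in table without corresponding event". In the schematic's first row (three years on bDMARD, two on tofacitinib, then an event), the censor-at-switch columns show 0/3 for bDMARD and 1/2 for tofacitinib.
- **Who switches in:** the section expects "most tofacitinib patients having been included in the bDMARD cohort prior to initiation of tofacitinib".

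**The concern.** Whether a patient's first 90 days on a new drug count for that drug is decided by whether the patient later has an event in them. For someone who switches to tofacitinib, those 90 days stay in the tofacitinib denominator if nothing happens. If a cancer or death occurs, both the event and the time leave. No tofacitinib event can be counted in that window, yet nearly all of its person-time is.

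The same rule acts in reverse when a patient leaves tofacitinib for another class. Events in the next 90 days are credited to tofacitinib, but the event-free leavers' time is not. The two errors pull in opposite directions and have no reason to cancel.

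The section relies on this analysis to show an early effect if latency is short. Those are the events that the rule moves, and most tofacitinib patients are expected to be affected at entry.

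**Working it through.** **Step 1. Which allocation does the schematic use?** Counting by hand with tofacitinib time from day 0 and bDMARD time to the switch gives the protocol's own entries (bDMARD, then tofacitinib): row 1, 0/3 and 1/2; row 4, 0/3 and 0/3; row 5, tofacitinib 0/4. Moving 90 days (about 0.25 y) for every switcher would give row 1, 0/3.25 and 1/1.75; row 4, 0/3.25 and 0/3; row 5, tofacitinib 0/4.25. The schematic therefore applies no lag, in agreement with the start and stop rules.

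**Step 2. Inputs.**

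- From section 9.5: 5% annual loss, constant accrual, malignancy 10/1000 PY, and 0% or 30% annual switching off tofacitinib ("Table 3 assumes a 30% annual rate of switching from tofacitinib to a bDMARD over the study period").
- Study length: 7 years in the list of assumptions but 5 years in the captions of Tables 2 and 3, so both were run.
- Window: W = 90/365.25 = 0.246 y.
- Share of starters who switch in, f: assumed 0.8 to 1.0, with 0.5 as a check, because the protocol gives no figure.
- No true drug effect, and constant hazards.

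**Step 3. Person-time per tofacitinib starter.** The total hazard of leaving the risk set is h = -ln(1 - switching) - ln(0.95) + 0.010. With 30% switching, h = 0.357 + 0.051 + 0.010 = 0.418.

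- Mean time on tofacitinib: PY = (1/h)[1 - (1 - e^(-hT))/(hT)]. For T = 7: (1/0.418) x [1 - 0.9464/2.926] = 1.62 y.
- E is the mean time within the first 90 days. It is slightly below W because of censoring.
- P is the mean time at risk in the 90 days after leaving. It is about 0.357 x 1.62 x 0.24 = 0.14 y at 7 years and 30%, and zero at 0% switching.

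**Step 4. Bias.** Tofacitinib loses the events in f x E and gains those in P, while its denominator stays almost unchanged. So observed/true = (PY - f x E + P)/PY.

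| Study length, switching | PY | E | P | Entry only, f = 0.8 to 1.0 | Net, f = 0.8 to 1.0 | Net, f = 0.5 |
|---|---|---|---|---|---|---|
| 5 y, 0% | 2.26 | 0.239 | 0 | 0.92 to 0.90 | 0.92 to 0.90 | 0.95 |
| 5 y, 30% | 1.39 | 0.228 | 0.117 | 0.87 to 0.84 | 0.95 to 0.92 | 1.00 |
| 7 y, 0% | 3.05 | 0.240 | 0 | 0.94 to 0.92 | 0.94 to 0.92 | 0.96 |
| 7 y, 30% | 1.62 | 0.230 | 0.138 | 0.89 to 0.86 | 0.97 to 0.94 | 1.01 |

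Example (7 y, 30%, f = 0.8): (1.619 - 0.184 + 0.138)/1.619 = 0.97. At the other extreme (5 y, 0%, f = 1.0): (2.263 - 0.239)/2.263 = 0.895. Results are almost the same at 6 and 30/1000 PY.

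**Step 5. Simulation check.** With 7 y, 30% and f = 0.9 at a true rate of 10/1000 PY, the rule as written gives 9.57/1000 PY. Moving the 90 days for everyone at both ends gives 10.00/1000 PY.

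**Step 6. bDMARD side.** The bDMARD cohort gains the early events without the event-free switchers' time. The schematic's note b bars entry to that cohort after tofacitinib, so patients leaving tofacitinib give no offset there. Take f = 0.8, and assume a mean bDMARD follow-up of 3.12 y (5% annual loss applied to that cohort over 7 years). The inflation is then 0.8 x 344 x 0.23/(11,100 x 3.12) = 0.2%, up to 0.8 x 1,000 x 0.23/(5,050 x 3.12) = 1.2%.

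**The case against.** **A lag for everyone may have been meant.** The opening of the sentence, which applies a 90-day risk window to the censoring-at-switch approach, can be read that way. The schematic is also drawn in whole years with no event within 90 days of a switch, so on its own it is weak evidence. This stands in part. But the explanatory clause in the same sentence is conditional on an event, and the start and stop rules independently give no lag. If a lag for all was meant, those rules and rows 1, 4 and 5 are wrong, and the section still needs reconciling.

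**The consequence is limited.** The analysis is secondary. With the 344 patients projected in section 9.5, about 344 x 1.62 x 0.010 = 5.6 malignancies would be expected, with a Poisson standard error near 42%. Entry removal at f = 0.8 is about 0.6 of an event before the exit offset. This stands as to size. It does not excuse a mismatch that costs only wording to remove.

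**The analysis plan can settle it.** The section leaves latency assumptions to that plan, but it states this allocation rule itself.

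**Stronger readings that a reader might infer.**

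- *The tofacitinib rate is 11-16% too low.* That is the entry end alone at 30% switching. It ignores the events that the same rule credits to tofacitinib after exit, and no net scenario above 11% was found.
- *The rate is always biased low.* At 30% switching and f = 0.5 the net ratio is 1.00 to 1.01.
- *This is the only malignancy analysis free of double counting.* The section also plans a sensitivity analysis restricted to bDMARD patients never exposed to tofacitinib.

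**Conclusion.** The mismatch is in the text: person-time is allocated by outcome, at both entry and exit. Under the protocol's own loss and switching scenarios, and assuming that 80-100% of tofacitinib starters switch in, the net tofacitinib rate is understated by about 3-11%: 3-8% at 30% annual switching and 6-11% at 0%. Near-zero bias when about half switch in at 30% switching is two errors cancelling by chance. The bDMARD rate is inflated by roughly 0.2-1.2%, which lowers a tofacitinib/bDMARD ratio slightly further.

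These sizes rest on constant hazards, uniform accrual and the assumed switch-in share. A reader might infer from the words tying the rule to the primary analysis that the main malignancy result is affected. It is not: once-exposed-always-at-risk follow-up does not stop at a switch. The point should be corrected before the final analysis, but it does not threaten the study's main result.

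**What to change.** In section 9.3.2, make the 90-day transfer unconditional and apply it at both ends. For every switcher, with or without an event, prior-therapy follow-up (bDMARD or tofacitinib) ends at switch + 90 days unless an event or another censoring reason comes first. New-therapy follow-up after a switch starts at switch + 90 days, among those still at risk. The alternative is to apply no transfer to anyone, so that events count for the new therapy from day 0.

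Under the first option, change the start and stop rules and rows 1, 4 and 5 of the schematic to match (values in Step 1 of the working). Under either option, correct the statement that the rule is part of the primary analysis.

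Both ends must change together. Lagging entry alone while keeping the event-based rule at exit would leave the tofacitinib rate about 10% too high at 30% switching: 0.138/(1.619 - 0.184) = 0.096 for 7 years and f = 0.8.

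The cost is wording and one schematic, with no new data. Under the first option, tofacitinib person-time in this secondary analysis falls by roughly the net share above, about 3-11%.
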